C.3.2. HWLs development. Given the ample evidence about the advantage of pictorial (text + image) over text-only HWLs (Hammond 2011, Noar 2016, b), we focused here on developing and testing the potentially most effective pictorial HWLs tailored to young WP users in Florida. Moreover, in the lab study, we are comparing HWLs on the device with no-HWL (control) to compare the suggested intervention with the status quo (no-HWL on the device). For HWLs placement on the device in Aim 2, we will follow FDA's and international recommendations

about HWL size (50% of principal display areas) (USDHHS. 2011, WHO FCTC 2011). Finally, in Aim 2 we are testing multiple (4) HWLs across different health themes to provide several options for HWLs application and rotation (Hammond 2009, a).

C.4. Aim 1: Adapt the 12 HWLs to young WP smokers in Florida using exploratory focus groups (Month 6 Year 1 - Month 6 Year 2). In this aim we will adapt the 12 HWLs that we developed in the Delphi study ([name] 2019) to our local population of young people in Florida through a 2-phase process; 1) conduct focus groups combined with a brief survey with member from the target population to obtain their feedback about the developed HWLs and how to enhance their design/effects and select the top-rated 4 HWLs from each theme, and 2) adapt and produce the 12 HWLs based on focus groups results to be used for dissemination (Aim 3), while the top-rated 4 HWLs will be tested in Aim 2 (Figure 8).

C.4.1. Phase 1: Conduct focus groups with young WP smokers in Florida. Available evidence emphasizes the importance of considering the target population's perception of HWLs messages (Hammond 2009, b). Therefore, using focus groups combined with a brief survey, this phase will allow us to adapt the 12 HWLs considering factors internal to our target population and WP smoking (e.g., beliefs, harm perception).

Objectives. This study aims to: 1) adapt and enhance the design/effects of the developed 12 HWLs based on the target population's feedback on the HWLs in term of attention (notice, engagement, general design), reaction (fear, believability, avoidance), effect (e.g. harm perception, intention to quit), and improvement (e.g. relatedness to participants, message clarity and synergy with pictorials); 2) *explore optimal placement and size of HWLs on each component (tobacco, device, charcoal)*, and 3) select the top 4 HWLs (one from each theme) based on participants' rating (Hammond 2011, WHO FCTC 2011).

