Interested WP smokers who call the phone number included in the study ad will be screened for eligibility, asked for contact information to confirm their participation and be given directions about the time/place of their focus group. Each session will start with a general discussion on the nature, confidentiality and general interaction mode for the group discussion. After explaining the study and obtaining written informed consent, participants will be provided with a set of forms, including a Baseline Assessment Questionnaire (demographic characteristics, WP smoking history, use of other tobacco products) and a stapled set of Individual Rating Sheets, one for each of the 12 HWLs (3 HWLs in each of the 4 themes) (Survey Instrument Section 1; Focus Groups Tool A, B, C & D). The focus groups discussion will then entail 4 segments of 15-20 min each (1 for each theme). Each segment will start with a PowerPoint presentation of theme-specific HWLs. Then, after viewing each theme's HWLs, a discussion will ensue about participants' reactions to the segment's HWLs in terms of 1- attention (notice, engagement, general design); 2- reaction (fear, believability, avoidance); 3- effect (harm perception, intention to quit); 4- improvement (relatedness to participants, message clarity, language level and synergy with pictorials); and 5- optimal placement (*size and durability of HWLs for each component - tobacco, device, charcoal*). After the discussion, participants will independently complete a rating question for each label by responding to the question "How effective is this HWL overall?" on a 10-point Likert scale (Thrasher 2012).

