Analysis. Focus groups sessions will be audio-taped and transcribed verbatim to assist in the coding of themes related to the discussion. Data will be analyzed using Dedoose Software version 5.0.11 (SocioCultural Research Consultants, 2016), which allows hierarchical linkage of codes for clear visualization of data structure. Two team members ([name], RA) will independently review transcripts and develop a consensus plan to identify recurring themes and variants. Coding, data reduction, display, and interpretation will be conducted using Creswell's 7-step analysis framework (Creswell 2009). Overlapping themes will be given greater emphasis. All initial codes and categories both within and across groups will be sorted and compared until core categories of recurrent themes emerge as a basis for Grounded Theory (Corbin 2014). In addition to comparing responses within and between groups, we also will evaluate differences in themes according to important participant characteristics, such as gender. To select the top HWL in each theme, we will calculate the sum of the text and picture rating score in terms of overall perceived effectiveness of each of the 3 HWL/theme and select the top-rated one (with the highest score). Thus, while the information from the discussions will give more detailed feedback about important communication domains and suggests further adaptation and improvements, analysis of the rating forms will provide a snapshot of how the HWLs are perceived in term of overall effectiveness and will help to select the top HWL in each theme to be tested in Aim 2.

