Design and Setting. Utilizing clinical lab methods, this aim provides broad testing of the top 4 HWLs on a myriad of WP smokers' subjective and objective outcomes. *We will recruit 2 groups of WP smokers (124 each, total 248; age 18-29 yrs) based on their use frequency (beginners: started WP smoking in the past 6 months, but smoke WP less than weekly; established: smoked at least once a week in the past 6 months) for a 2x2x2x4 within-subject (2: HWL vs no-HWL x 2: pre- vs post- smoking) and between-subject (2: beginner vs established smokers x 4: HWLs) experimental study. Participant in each group (beginner, established smoker) will be randomly assigned to one of the 4 HWLs conditions, and undergo 2 WP smoking sessions that differ by HWL on the WP device (HWL vs. no-HWL), with pre-/post-smoking assessment of harm perception, intention to quit, puffing behavior, satisfaction, urge to smoke, and toxicant exposure (CO, nicotine, oxidative stress) (Figure 9). We will use Latin Square crossover design balanced for carry-over effect (random order of 4 HWL condition), and to ensure equal distribution of study participants across gender. Accordingly, every subject will undergo 2 WP smoking sessions in the clinical lab setting differing by label (HWL vs. no-HWL) in a balanced random sequence; the same number of subjects gets each label and its order (1st or 2nd session) the same number of times, and for each gender. As in (Evans 2015, Brewer 2016, Brewer 2019), all participants will receive a follow-up phone call assessment after 3 months of the last session to evaluate the longer-term effect of exposure to the HWLs in real-world setting including HWLs recall, social interactions about WP harms (talk about HWLs with family/friends), and behavioral adaptations in response to exposure to HWLs (e.g., harm perception, quit intention, quitting).*

Such an approach allows:

- 1- Thorough comparisons without the need for large samples using powerful within-between subjects design.
- 2- Comparative testing for HWLs with current practice (no label control).
- 3- Comparative assessment of the 4 HWLs, and the themes they represent, on important

outcomes through between-subjects pre-post analysis.

4- Assessment of the expected effect of HWLs on WP smokers at different stages of their smoking trajectory.

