to-medium effect size (Cohen's $f=0.19$) depending on HWL condition ([name] 2019, b). *This study will include 248 WP smokers (124 beginners; 124 established) randomized to 4 groups (62 each) along the 4 tested HWLs. Using repeated measures ANOVA F test with 2 within and 2 between factors, a total sample size of 240 participants will have at least 80% power to detect small-to-medium size effect (Cohen's $f=0.2$) or larger for $2 \times 2 \times 2 \times 4$ within-subject (H WL condition and time) and between-subject (smoking frequency and 4 different HWLs) effects, as well as their interactions at 0.05 level of significance, assuming sphericity and a moderate correlation (0.5) among repeated measures (Cohen 1988). The proposed sample size will provide sufficient power to detect small to medium effects expected based on our pilot data ([name] 2019, b). It is also feasible as we have not encountered any difficulty in recruiting a large number of WP smokers in our lab studies ([name] 2019, a).*

Screening, Informed Consent. Individuals who are identified as potentially eligible based on the phone screening will be asked to attend an onsite-screening, which will involve assessment of inclusion/exclusion criteria, physical examination, and urine pregnancy testing for women. Prior to screening, potential participants will undergo a review of the study and consent procedures to ensure that they understand the study, its risks/benefits, and their rights as research participants. Consented (written) individuals will then undergo a physical examination conducted by the research nurse, who will have access to an on-call Medical Monitor (physician) in case of concern or for consultation at any point of the study as it is the standard practice in our lab ([name] 2019, a, [name] 2019, b). The physical examination will include measuring BP, heart rate, temperature, pulse oximetry, and weight/height. Successfully consented/screened participants will be scheduled for their 1st session and asked to abstain from all tobacco use 12 hours prior to it.

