Experimental Methods. Participants will be randomly assigned to one of the 4 HWLs conditions and attend the lab for two, ~2-h sessions, separated by a 48-h washout period, and differ by HWL on the device (H WL vs. no-HWL control). Session order will be randomly counterbalanced to avoid order effects; counterbalancing also will allow us to study the effect of HWL on smoking behavior prospectively (i.e. between sessions difference is expected to be less when the HWL condition is tested first). They will also be balanced across the 4 HWLs (62 sessions for each HWL) to allow for equal numbers and robust comparisons of the 4 HWLs and their representative themes.

At the beginning of the 1st session, participants will provide demographic and personal information including age, socioeconomic status, race/ethnicity, and detailed tobacco use history, especially WP use. Then abstinence will be verified by eCO<5 ppm. Those who have eCO>5 ppm will be rescheduled. Those who are abstinent will get familiarized with the study procedures, measures, and they will be given time to adapt to the lab.

After adaptation, continuous measurement of physiological responses begins, and 10 ml of venous blood is sampled, and participants are asked to respond to subjective measures (pls. see below Outcome Measures). They will then begin a maximum 45 min WP smoking session (time recorded) using a device fitted with the pre-selected HWL or no-HWL according to condition. The HWL will be placed in a constant location/size on the device, which will be placed in front of participant seat (at vision level). For each participant, preferred brand/flavor of WP tobacco (verified at screening) will be used to neutralize the effect of nicotine/flavor on study outcomes. We will follow our tested lab protocol developed to study the WP (Ben Taleb 2018), where prior to each session, the lab staff will pack the WP head with 15 g of the participant's favorite tobacco preparation and cover it with perforated foil. Tobacco will be heated with quick-light charcoal disks (33 mm diameter; 6.2 g; Three Kings, Holland, or similar brand). Initially, a single charcoal disk will be used, and several (pre-weighed) ½ charcoal disks will be made available to the participants so they can add *ad libitum* (Cobb 2012). The timing of each

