
Impact. This study will provide robust testing of the HWLs, and their themes, on a variety of outcomes that are important to assess the potential of HWLs on WP use and popularity among young people in Florida. It will also provide tested HWLs for further dissemination and implementation within the state and nationally.

C.6. Aim 3: Communicate the knowledge obtained to advance WP control in Florida and nationally (Year 1 - 5). *Concerns about our dissemination strategy and its target audience and outcomes necessitate clarifying that the main audiences for our proposed work are policymakers, regulators, and policy advocates, while young WP users are the ultimate target population when the HWLs are implemented. For this purpose, our partnership with Golin is optimal as they have extensive experience in advocacy for public health policy through their work with the Florida Dep. Health, CDC, and others. Still, in response to the review, we now expanded our dissemination to include young adults in collaboration with Truth Initiative, which has extensive experience in tobacco control advocacy focusing on youth. Truth Initiative will use the messages and images we developed in their counter-tobacco campaigns, and evaluate them for further message development and fine-tuning (e.g. [name] et al., 2017; Hair et al., 2017). We are also involving FDA staff, such as past policy director at the FDA Center for Tobacco Products to guide our team on the legal aspects of applying HWLs to the WP.*

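### Aim 2 tests a single label per theme, so theme and label are the same variable and the stated comparison of themes cannot be made

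*Combined protocol and SAP*

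**What the plan says.** **Selection of labels (C.4.1).** Under Procedures, focus-group participants receive rating sheets, "one for each of the 12 HWLs (3 HWLs in each of the 4 themes". Under Objectives, the aim is to "select the top 4 HWLs (one from each theme". The Analysis paragraph takes the highest summed rating within each theme and says the rating forms "will help to select the top HWL in each theme to be tested in Aim 2".

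**Design and model (C.5).** Under Sample Size, the 248 participants are "randomized to 4 groups (62 each) along the 4 tested HWLs". Under Statistical Analysis, the primary model has one four-level between-subject factor for label assignment. There is no theme term and no term for label within theme.

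**Statements about themes (C.5).** There are three:
- Design and Setting lists among the things the approach allows: "Comparative assessment of the 4 HWLs, and the themes they represent, on important" outcomes.
- Experimental Methods says sessions are balanced across labels "to allow for equal numbers and robust comparisons of the 4 HWLs and their representative themes".
- The Impact paragraph says: "This study will provide robust testing of the HWLs, and their themes, on a variety of outcomes".

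Nowhere do the documents say that theme and label cannot be separated, or limit the conclusion to the four labels tested.

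**The concern.** A theme is a class of messages, and a label is one picture with one text from that class. To learn about a theme, one must see how much labels differ within it, and that needs at least two labels per theme. Here each theme is represented by one label, which is also the best-rated of three rather than a typical member. A difference between two labels could arise from the image or the wording, and nothing in the data can tell this apart from an effect of the theme.

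The plan's own Aim 1 treats labels within a theme as unequal. It ranks them, keeps one, and collects feedback on design, clarity and the fit of text to picture.

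At stake is what may be concluded. All twelve adapted labels go to dissemination under C.4.2, and eight of them are not tested in the lab. A result worded as a theme effect could be carried over to those eight without support.

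**Working it through.** **Inputs from the documents.** 4 themes with 3 labels each; 1 label per theme in Aim 2; 248 participants, 62 per label; alpha 0.05; Cohen's f = 0.2; correlation 0.5; 2 x 2 within-subject and 2 x 4 between-subject factors (m = 4 measurements, k = 8 groups).

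**1. The plan's own figure.** For a between-subject effect, lambda = N f² m / (1 + (m − 1) rho). With N = 240:

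lambda = 240 × 0.04 × 4 / (1 + 3 × 0.5) = 38.4 / 2.5 = 15.36.

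Power is 0.818 for the eight-group effect (7 and 232 df) and 0.919 for the four-level label effect (3 and 232 df). Within-subject effects and interactions have at least 0.999. The stated minimum of 80% at N = 240 is reproduced. It is power to detect differences between labels and has no bearing on whether such a difference can be assigned to a theme.

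**2. Can theme be separated from label?** Compare the rank of the design matrix with theme terms, with label terms, and with both. The df for label within theme is rank(both) − rank(theme).

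| Labels per theme | Participants per label | Rank: theme / label / both | df, label within theme |
|---|---|---|---|
| 1 (as planned) | 62 | 4 / 4 / 4 | 4 − 4 = 0 |
| 2 | 248 / 8 = 31 | 4 / 8 / 8 | 8 − 4 = 4 |
| 3 | 248 / 12 = 20.7 | 4 / 12 / 12 | 12 − 4 = 8 |

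As planned, the theme columns and the label columns are identical. No covariate adjustment or mixed model can change that.

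**3. Illustration of size.** The documents give no SD between labels of the same theme. Assume a value tau, in SDs of the paired difference between labelled and unlabelled sessions, and no true theme effect. If labels are random draws, the F statistic of the four-group test (3 and 244 df, critical value 2.64) is inflated by 1 + 62 tau², so

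P(reject) = P(F > 2.64 / (1 + 62 tau²)).

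The last column is a simulation in which the best of three normally distributed labels is kept in each theme and the ratings predict the lab effect perfectly. Selection then shrinks the spread of the retained labels to about 0.75 tau.

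| tau | 1 + 62 tau² | 2.64 / (1 + 62 tau²) | Random label | Best of three |
|---|---|---|---|---|
| 0 | 1.00 | 2.64 | 5.0% | 5.0% |
| 0.1 | 1.62 | 1.63 | 18.3% | 12% |
| 0.2 | 3.48 | 0.76 | 51.8% | 35% |
| 0.3 | 6.58 | 0.40 | 75.2% | 59% |

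**4. Does a larger sample help?** The sampling SE of a difference between two labels is sqrt(2 / 62) = 0.18 and falls with n. The part due to label choice is sqrt(2) × tau = 0.14, 0.28 or 0.42 and does not. With 124 per label the inflation factors become 2.24, 5.96 and 12.16, and the random-label rates rise to 32%, 72% and 89%.

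**The case against.** **Theme is not a formal target.** This stands. The Aim 2 hypotheses concern labelled versus unlabelled sessions and beginners versus established smokers. C.3.2 gives the reason for testing four labels as having several options for use and rotation. A reader might infer that a planned primary test is invalid. The documents do not support that, because no theme test is specified and both the labelled-versus-unlabelled contrast and the randomized comparison of the four labels are sound.

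**The wording can be read mildly.** In part. Only Experimental Methods speaks of robust comparisons. Design and Setting speaks of comparative assessment, and Impact of robust testing. The first two could mean comparing the best representative of each theme, which the design does estimate. But theme appears in all three places without that qualification.

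**Presentation on the device is controlled.** This stands. Experimental Methods holds the label's location and size constant, so the confounding is with picture and wording, not placement.

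**The harm is not documented.** This stands. A reader might infer that theme rankings will be reported to regulators. No section says so, and dissemination of the twelve labels does not depend on a theme result. Misuse is possible, not planned.

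**The rates are not anchored.** This stands. If the pilot's f = 0.19 is read as a two-condition effect with correlation 0.5, the whole label effect is about 2 × 0.19 = 0.38 SD of the paired difference. A tau of 0.3 is then 0.3 / 0.38, about 79% of it, which is an extreme case. Also, the rejections are correct detections of differences between labels; they become errors only when renamed as theme effects.

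**Aim 1 covers three labels per theme.** It does, but only for focus-group reactions and perceived effectiveness, not for the lab outcomes. A phrase in the C.4 overview could be read as four labels from each theme, but only three exist and the other sections fix one.

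**Conclusion.** The point holds as a matter of identifiability, and that part needs no assumption: one label per theme leaves 0 df for label within theme. The three statements in C.5 therefore claim a property the design does not have.

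The size is illustrative only. For an assumed tau of 0.1 to 0.3 and no true theme effect, reading the label test as a theme test would mislead in about 12% to 59% of studies under perfect best-of-three selection, and in about 18% to 75% with randomly drawn labels, against 5%. How well ratings predict lab effect is unknown; under the normal model used here, imperfect prediction would fall between the two. These figures should not be taken as the type I error of any test in the plan.

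The sample size, the primary model and the two valid comparisons are unaffected.

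**What to change.** In C.5, amend Design and Setting (the listed advantage on comparing the labels), Experimental Methods (the sentence on balance across labels) and Impact. Restrict the comparison and its conclusions to the four labels tested, and state once that differences between themes cannot be inferred with one label per theme.

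This changes wording only. Arms, sample size, outcomes and analysis stay as they are. The cost is giving up a claim the design cannot support.

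If theme inference is really wanted, at least two labels per theme would be needed, with label nested in theme. That is a different trial: 31 participants per label at N = 248, and only 4 df for the theme test's error term if labels are treated as random.

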5. Change in WP smoking will be asked at 3-month assessment using 3 items; “*Since you started the study, 1- did you stop smoking for 1 day or longer because you were trying to quit WP smoking?, 2- did you avoid smoking WP because you were thinking about the HWLs?, and 3- did you stop WP smoking completely because of the HWLs?*” (Brewer 2016).
6. Toxicant exposure includes eCO, plasma nicotine, and EBC oxidative stress.
 - eCo will be measured initially at the beginning of the smoking session (abstinence verification), and within 10 min after the WP smoking session via e-CO monitor (Vitalograph, Lenexa, KS).
 - Plasma nicotine will be assessed pre-/post-smoking. The research nurse will draw Blood samples (~ 10 ml) via a butterfly needle from a forearm vein before smoking session onset and within 10 minutes of its end. Research staff will centrifuge blood samples and freeze plasma immediately, to be analyzed later by Forensic Chemistry Lab at FIU using Liquid Chromatography Mass Spectrometry.
 - Exhaled Breath Condensate (EBC) will be collected pre-post smoking session to test for markers of oxidative stress and DNA damage. We will test for 6 biomarkers (8-oxodGuo, 8-oxoGuo, 8-isoprostanate, formaldehyde, acetaldehyd and malondialdehyde) (Gong 2013, Hu 2015). Samples will be collected during 15 min of tidal breathing through a single-use disposable RTube TM collector (Respiratory Research, Inc., Charlottesville, Va., USA). After sample collection, a plunger will be used to pool the condensed material within the tube into a single sample (about 1.0-2 ml). EBC samples will be divided in aliquots and stored at -80°C. EBC samples will be analyzed by our Forensic Chemistry Lab at FIU using Online Solid-Phase Extraction and Liquid Chromatography Triple Quadrupole Mass Spectrometry (LC-QqQ-MS) and Gas Chromatography Mass Spectrometry (GC-MS) (Hu et al., 2015; Gong et al., 2013). malondialdehyde) (Gong 2013, Hu 2015).

7. Puff topography will be assessed continuously during smoking. It will be measured with a device that was developed by Shihadeh (Shihadeh 2005b), and validated in several WP studies ([name] 2009, Cobb 2015). Briefly, a pressure transducer is integrated into the WP hose, and inhalation-induced pressure changes are amplified, digitized, and sampled at a rate of 1000 Hz. The software converts signals to airflow (ml/sec) and integrates the flow data, producing measures of puff volume, duration, number, and interpuff interval (IPI).

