Statistical Analysis. Prior to analysis, physiological data will be averaged to produce a single baseline value for each measure (10 minutes prior to WP use) and for each 10- minute that a participant was actually using the WP. Topography data will be processed automatically by the topography instrument software to eliminate closely spaced puffs (i.e., IPIs < 300 msec). Such puffs are assumed to be part of the previous puff and the recorded volume and duration values will be added to that preceding puff ([name] 2009). After this procedure, any puffs less than 5 ml will be considered an artifact and automatically discarded. Remaining data will be averaged for each participant in each condition using all remaining values for puff volume, duration, number, and IPI (Shihadeh 2004). We will address the issue of stability of WP puff topography by correlating topography values across sessions (Shihadeh 2005a). For plasma nicotine, values below the limit of quantitation (LOQ) will be replaced with the value of the LOQ ([name] 2011). Demographical data will be examined to determine if there are significant between-group differences on measures that may be related to study outcome (some differences are expected due to design such as past 30-day WP use) though these are expected to be minimized as a virtue of randomization. Unexpected between-group differences will be considered as potential adjustment covariates in the primary analysis (Evans 2006). *The primary analysis of each outcome will involve a 4-factor analysis of variance (or covariance) with two within-subject factors; HWL (HWL vs. no-HWL/control) and time (pre-post smoking), and two between-subject factors; smoking frequency (beginner vs. established WP smokers) and HWL (4 group assignment). This approach will be extended into mixed-effects linear regression model in order to adjust for potential confounders such as gender, education, race, SES, and self-efficacy. To assess if gender has any effect on the results, it will be considered as a covariate and we will test the pre-planned interaction with it to determine heterogeneity of HWL by gender as well as potential differential effects.* We will test for carry over effect statistically and will control for it when testing for the primary factors (Senn 2002). Significance levels will be adjusted for violations of the sphericity assumption using Huynh-Feldt corrections (Keppel 1991). The mean square error terms for the overall interaction will be used to conduct Tukey's honestly significant difference test (Keppel 1991), with comparisons at $P < 0.05$ considered significant.

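### The three listed 3-month items on change in waterpipe smoking cannot give the amount or net direction of change in use, and no repeat measure of use is described

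*Combined protocol and SAP*

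**What the plan says.** Section C.5, Outcome Measures, item 5 defines change in waterpipe smoking at 3 months by three questions, each covering the period from study entry onward:

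1. Quit attempt: "did you stop smoking for 1 day or longer because you were trying to quit WP smoking"
2. Avoidance: whether the person kept away from the waterpipe with the labels in mind.
3. Complete stopping: "did you stop WP smoking completely because of the HWLs"

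The other measures listed for the call are harm perception, intention and motivation to quit, recall, and conversations about the labels (items 1 to 4).

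Design and Setting enrols 124 beginners, who "started WP smoking in the past 6 months, but smoke WP less than weekly", and 124 established smokers, who "smoked at least once a week in the past 6 months". The established group has no stated upper limit.

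Use is recorded at entry. Experimental Methods takes a "detailed tobacco use history, especially WP use" at the first session, and Statistical Analysis refers to past 30-day use as a measure on which the groups will differ: "some differences are expected due to design such as past 30-day WP use".

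On purpose, Design and Setting says the call looks at adaptation in response to the labels, including quitting. Specific Aims (Aim 2) describes it more broadly, as assessing later change in attitude to quitting and in behaviour. The model in C.2 ends with reducing or quitting smoking.

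**The concern.** The threshold in item 1 suits people who smoke every day. The source cited for item 5 is listed in the References as a trial of cigarette pack warnings, and no adaptation to intermittent use is described, although A.4 itself stresses that waterpipe use is intermittent and unlike cigarette use. For an occasional smoker a smoke-free day is the usual state, so the answer depends on recalled motive, and intention to quit is already asked separately at the call.

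Items 2 and 3 make the respondent decide what caused the behaviour. Someone who cut down without crediting the label answers no to both, and an increase in use cannot be recorded by any of the three. Item 3 is the only question about stopping completely, and it carries the cause inside the question.

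At stake is the behavioural end of the conceptual model. The study could report how many people say a label made them avoid or stop smoking, but not whether use went down, by how much, or whether it differed among the four labels.

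**Working it through.** The plan states no figure to reproduce. The check sets item wording against the use frequencies that define the groups.

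**Step 1: how often the one-day duration is met without any change.**
Inputs: the weekly boundary between the groups (Design and Setting), and 3 months taken as 90 days. Let s be sessions per week, with at most one session a day.

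Smoke-free days in 90 = 90 × (1 − s/7)

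| s (sessions per week) | Source | Smoke-free days of 90 |
|---|---|---|
| 1 | group boundary | 90 × 6/7 = 77.1 |
| 2 | assumed | 90 × 5/7 = 64.3 |
| 3 | assumed | 90 × 4/7 = 51.4 |
| 5 | assumed | 90 × 2/7 = 25.7 |
| 6 | assumed | 90 × 1/7 = 12.9 |

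A beginner is below s = 1 and so has more than 77 such days. The duration part of item 1 is met by all beginners (124/248 = 50%) and by every established smoker below daily use. Only for daily smokers can it discriminate. The plan does not give the distribution of use among established smokers, so their share cannot be computed.

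**Step 2: what each item can and cannot show.**

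| Item | A yes requires | What it cannot show |
|---|---|---|
| 1 | a stop of a day or more, and a motive of trying to quit | for non-daily smokers, anything beyond the motive; whether the stop lasted |
| 2 | avoidance, credited to the label | how much was avoided; reduction for other reasons |
| 3 | complete stopping, credited to the label | stopping for other reasons |

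None can record an increase, and none gives a frequency.

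**Step 3: can change be computed from baseline?**
A use history is taken at session 1. No matching measure appears among the items listed for the call, so there is nothing at 3 months to set against it.

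**Step 4: would a plain 30-day abstinence question be enough?**
Not alone. The beginner definition has no stated lower limit on frequency. If sessions occur at random at a constant rate (an assumption), the chance of none in 30 days is exp(−s × 30/7):

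- s = 1: exp(−4.286) = 0.014
- s = 0.5: exp(−2.143) = 0.117
- s = 0.25: exp(−1.071) = 0.343

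An unchanged smoker at one session a month (s of about 0.25) would look abstinent about a third of the time. Abstinence has to be read against the person's own baseline frequency.

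**Step 5: which contrast is randomised at 3 months?**
Every participant has a labelled and an unlabelled session, so no one is unexposed at the call. The randomised contrast in label content is among the four labels, 248/4 = 62 each.

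**The case against.** The strongest reply is that the items do what Design and Setting asks: they record adaptation in response to the labels. Avoidance and stopping credited to a label are self-reported behaviours and can be compared across the four labels. That stands, and it limits the point. A reader might infer that the items measure no change at all, or that the call has no behavioural endpoint; the documents do not support that.

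A reader might also infer that anyone who smokes less than daily meets item 1. That is wrong. The item also requires that the stop was made in trying to quit, and a non-daily smoker who was not trying should answer no. Only the duration part is met automatically, and the arithmetic above says nothing about how often the whole item misclassifies.

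Nor are people who quit for reasons other than the label invisible. Item 1 does not mention the labels, so a deliberate quitter can answer yes there and no to item 3. What is lost is whether that attempt lasted, stopping without a deliberate attempt, and any reduction or increase not credited to the label.

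It would also go too far to say that current use is not asked at 3 months. Outcome Measures refers to Table 1 and a Survey Instrument, which were not available for this review. The supportable statement is that no repeat item is described in the text. The exact wording of the session-1 question is likewise not shown.

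Finally, the call is supplementary. The sample size rests on exhaled carbon monoxide, and the described primary analysis compares sessions in the lab. This bears on priority; it does not fill the gap, because Specific Aims and C.2 look beyond attributed change.

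**Conclusion.** The point holds in a limited form. From the three listed items, neither the amount nor the net direction of change in waterpipe use can be estimated. The one-day threshold carries no information beyond stated motive for all 124 beginners (50% of 248) and for an unknown number of established smokers who smoke less than daily. Items 2 and 3 capture only label-attributed change.

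This rests on the group definitions, on counting at most one session a day over 90 days, and on no repeat use measure being present in Table 1 or the Survey Instrument. If one is there, the remaining need is to list it as a 3-month outcome and say how it will be analysed. The main in-lab inference is not affected; this is a worthwhile, inexpensive improvement to a supplementary outcome.

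**What to change.** - At the 3-month call, repeat the session-1 waterpipe frequency question in the same words. Compare 3-month use across the four randomised labels, adjusted for baseline use and smoker group. Adjustment matters because beginners start low and have less room to fall than frequent established smokers.
- Ask about current abstinence without a cause clause, and interpret the answer against the person's baseline frequency.
- Keep the three existing items, reported separately: item 1 as a self-reported quit attempt, items 2 and 3 as label-attributed change. This preserves comparability with their source.
- State that only the between-label contrast is randomised at 3 months, and report overall change from baseline as descriptive.

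Cost: about one extra minute per call and a minor instrument amendment. No change to recruitment, the lab sessions or the main analysis is needed. The change should be made before calls begin, since use at 3 months cannot be reliably recovered later.
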